| Objectives | Primary Objective: Verify whether non-sedated 3D volumetric structural magnetic resonance imaging (MRI) obtained in the first 4- 12 weeks of life can reliably discriminate between brachial plexus birth palsy (BPBP) injury patients who require surgical reconstruction versus those who will recover spontaneously. Secondary Objective 1: To assess whether MRI findings for pre-operative planning in infants with BPBP, specifically the level(s) and extent of injury of each nerve root and the location of root injury (pre- vs. post-ganglionic), correlate with intraoperative findings identified during brachial plexus reconstructive microsurgery. Secondary Objective 2: Two standard BPBP clinical measures – the Active Movement Scale (AMS) and Toronto scores will be used to confirm clinical outcomes of our decision-making both for and against surgery. |
| Statistical Methodology | The primary analysis for this will be assessing the discriminant ability of the SRS system to distinguish patients who do versus do not go on to surgery, by estimating the area under the receiver operating characteristic (ROC) curve with a 95% confidence interval. |

Study Schema

1.0 Introduction:

1.1 Background

Brachial plexus birth palsy (BPBP) affects approximately 1 in 1,000 children at birth, and though the majority of infants regain full function of the affected arm, many of these injuries result in lifelong disability. Varying degrees of BPBP, from mild (neuropraxia) to severe (post-ganglionic root rupture or pre-ganglionic root avulsion), are indistinguishable on the initial clinical exam. Serial clinical examination is the current gold standard for separating infants who will recover spontaneously from those who will need reconstructive surgery. Unfortunately, this "wait and see" period may last for up to 6 months, and the effectiveness of surgery can decrease during this time. The surgeon must balance the fact that 60-80% of infants with BPBP will recover spontaneously without surgery with the knowledge that earlier nerve repair improves outcomes for infants with more severe injuries. A non-invasive diagnostic test which differentiates these two groups of infants with BPBP within weeks of birth may help improve surgeons' prognostic accuracy and therefore the treatment of this disorder. In addition, currently surgeons rely on operative exploration, visual inspection and somewhat non-specific somatosensory evoked potentials (SSEPs) to differentiate pre-ganglionic and post-ganglionic injuries, which have completely different surgical treatments. A pre-operative test that provided accurate and specific diagnosis of each root injury would improve pre-operative planning and accuracy of treatment.

We have developed a rapid (<10 minute imaging acquisition) volumetric magnetic resonance imaging (MRI) sequence with high spatial resolution and soft tissue contrast that does not require sedation or administration of a contrast agent and provides an accurate assessment of the level and severity of both pre- and post-ganglionic BPBP injuries [1]. The pilot data we acquired on 9 infants demonstrates the ability of this imaging protocol to distinguish those infants who went on to surgery at 6 months of age from those who made a spontaneous recovery. Additional study enrollment would validate the ability of imaging protocol to differentiate between operative and non-operative injuries, which would benefit both groups: first, those with injuries who do require surgery could potentially be reconstructed earlier and more accurately, and second, families of the majority of infants who will recover spontaneously could be spared months of worry. Our research goal is to recruit a total of 100 patients over a 5-year period yielding at least 70 evaluable patients at three institutions (Shriners Northern California, Boston Children's Hospital, and Gillette Children's Specialty Hospital) utilizing the same imaging, serial clinical exams, and surgical protocols as our pilot study.

1.2 Risks, Benefits and Alternatives

1.2.1 Risk Category

This study is no greater than minimal risk. Subjects will not encounter risks greater than those they would encounter in daily life.

1.2.2 Potential Risks

1.2.2.1 There is a small risk of loss of confidentiality.

1.2.2.2 While there is no known direct effect of high static magnetic field strength, there are secondary safety considerations of the static magnet field to consider, namely the possibility that medical equipment (for example, pacemakers) will malfunction in the magnetic field, or that the magnetic force exerted by the static field will cause motion of ferromagnetic materials (either implanted or external to the body). These are standard issues involved in MR imaging, and we already have procedures in place to address them for imaging. MRI safety is documented by screening the patient prior to scan and by completing a questionnaire prior to scan. The risks are reasonable in that the anticipated benefits and/or knowledge gained from the results of this study could determine other medical treatments that provide a better clinical outcome.

1.2.3 Protection Against Risk

1.2.3.1 Data collected will be recorded in such a manner (coded) that subjects will not be identified. The key code and all study documents with coded data (such as case report forms) will be stored in a locked cabinet file and/or password-protected computer file in an access controlled office only accessible to research personnel. Information about study subjects will be kept confidential and managed according to the requirements of the Health Insurance Portability and Accountability Act of 1996 (HIPAA).

1.2.3.2 MRI safety is well documented in neonates. Additional risks are further reduced by preformatting the MRI with swaddling and MRI safety questionnaire and screening prior to the scan. To eliminate the risk of injury from external objects, there will be a “zero-tolerance” policy for ferromagnetic materials in the scan room during patient scans. Subject’s parent/guardian will remove all ferromagnetic items (jewelry, pocket contents, belt buckles, footwear with steel nails or toe covers, etc.) before entering the magnet room, and only non-magnetic equipment will be allowed within the scan room. All subjects are subjected to a metal detector screening (similar to that performed at airport security booths) before being permitted to enter the scanning suite.

1.2.4 Potential Benefits to the Subject

The results from this study could benefit future patients by providing an earlier stratification of injury severity and the opportunity for earlier surgery for those who may need it.

1.2.5 Alternatives to Participation

The patient can choose to not participate in the study and they will continue to receive standard care at the research site.

2.0 Objectives:

2.1 Objectives

2.1.1 Primary Objective

Verify whether non-sedated 3D volumetric structural magnetic resonance imaging (MRI) obtained ≥ 28 days and ≤ 4 months old can reliably discriminate between brachial plexus birth palsy (BPBP) injury patients who require surgical reconstruction versus those who will recover spontaneously.

2.1.1.1 Hypothesis:

The SRS will effectively be able to discriminate between infants who require surgical reconstruction versus those who will recover spontaneously.

2.1.2 Secondary Objective 1:

Assess whether MRI findings for pre-operative planning in infants with BPBP, specifically the level(s) and extent of injury of each nerve root and the location of root injury (pre- vs. post-ganglionic), correlate with intraoperative findings identified during brachial plexus reconstructive microsurgery.

2.1.2.1 Hypothesis:

MRI findings for pre-operative infants will exhibit characteristics similar to those found intraoperatively.

2.1.3 Secondary Objective 2:

Two standard BPBP clinical measures – the Active Movement Scale (AMS) and Toronto scores will be used to confirm clinical outcomes of our decision-making both for and against surgery.

2.1.3.1 Hypothesis:

AMS and Toronto scores will improve to functional levels at final follow-up for those subjects who were determined not to need surgery. AMS and Toronto scores will improve following surgical intervention for those subjects who undergo surgery.

3.0 Subject Selection:

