4.3 Study Procedures

4.3.1 Study Visits

At the baseline visit, we will collect patient demographics, prenatal and perinatal history, as well as information on any concomitant birth injuries. A standardized physical examination will be conducted at the enrollment visit and all subsequent study visits, consisting of the Toronto Score and AMS score. The Narakas score and the MRI will take place at or around the time of enrollment into the study. At the time of the MRI scan, the neuroradiologist will document the status of each nerve root as normal, post-ganglionic rupture, or pre-ganglionic avulsion, in addition to calculating the numerical SRS. For those infants who undergo microsurgery, we will document the indications for surgery, operative findings at each nerve root, and procedure performed at each nerve root.

[figure not shown]

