Each subject's MRI scan will be reviewed independently by neuroradiologist investigators. The neuroradiologists will interpret the MRI scan and report their findings in the medical record as per standard clinical protocols. Surgeons and families will be aware of these findings and will be able to view the images. However, the SRS calculation will be performed outside the medical record and will not be available to surgeons until after data collection is completed in order to minimize bias. Our pilot data demonstrated inter-rater reliability (Krippendorff's alpha) of 0.78 for calculation of the SRS. The neuroradiologist investigators at the other study centers will read and calculate SRS scores for the pilot study subjects with the goal of exceeding an inter-rater reliability of 0.75 with the other neuroradiologists prior to testing study subjects. In addition, during the study period, a subset of MRI scans will be de-identified and shared between institutions for the purposes of inter-observer and intra-observer analysis. Figure 1 illustrates the calculation of the SRS score from the MRI findings. Each injured level is first assigned 1 point, with additional points assigned for pre-ganglionic injuries: 2 points for each absent nerve rootlet, 2 points for each pseudomeningocele, 0.5 points for each abnormal nerve rootlet; and for post-ganglionic injuries: 1.5 points for each neuroma and 0.5 points for each abnormal nerve. If the zone of injury includes both the pre- and post-ganglionic regions, only the pre-ganglionic injury is scored. The total radiologic score ranges from 0 points (no evidence of nerve root injury on MRI) to 25 points (all 5 levels with pre-ganglionic pseudomeningoceles and absent nerve rootlets). In addition, the neuroradiologist will score each nerve root level as intact, post-ganglionic rupture, or pre-ganglionic avulsion. This information will then be compared with the findings at surgery as described above for those infants who undergo surgery.

Figure 1. Calculation of the Shriners Radiological Score (SRS)

4.3.2.1 Subjects who do not complete the scan or end up with unusable images can repeat the MRI up to two additional times as long as they are within the eligibility window.

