4.3.3 Surgery

The decision to proceed to surgery will be made by the operating surgeon using the accepted standard clinical indications. These are: 1) flail arm and Horner's syndrome 2) Toronto score less than 3.5, 3) failure to recover antigravity elbow flexion and/or antigravity shoulder abduction (AMS score for elbow flexion and/or abduction less than 5), 4) failure to bring the hand to the mouth (cookie test), or other clinical indication of lack of appropriate nerve recovery. For those infants in the study who undergo microsurgical plexus exploration, the status of each nerve root will be recorded by the operating surgeon as intact, postganglionic rupture, or pre-ganglionic avulsion. This status will be determined based on the intraoperative appearance of the nerve root as well as intraoperative SSEP testing as follows: avulsed (no repeatable response with maximal stimulation), ruptured (repeatable response to SSEPs but without distal motor function), or intact (repeatable response to SSEPs with distal motor function).

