8.0 Statistical Considerations

8.1 Primary Study Endpoints

The primary endpoint is the surgeon's decision for or against surgery, typically made by 6 months of age. Surgeons will make their decision based on all available clinical data, including the MRI, but will be blinded to the neuroradiologist's scoring of the SRS and its components.

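### Uncontrolled post-operative gains in AMS and Toronto scores cannot confirm a decision for surgery, and the recorded operative findings are not used as a check on the operated group

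*Combined protocol and SAP*

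**What the plan says.** Section 2.1.3 states that the two scores "will be used to confirm clinical outcomes of our decision-making both for and against surgery". Its hypotheses are not symmetric. For infants managed without surgery: "AMS and Toronto scores will improve to functional levels at final follow-up for those subjects who were determined not to need surgery". For operated infants: "AMS and Toronto scores will improve following surgical intervention for those subjects who undergo surgery". The second sets no functional level, no amount of change and no comparator.

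Section 8.4 uses the 18- and 30-month scores to confirm spontaneous recovery in the non-operative group, then compares them with the surgery group's scores at the same ages. It describes no other analysis of the operated infants' scores.

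The primary endpoint (8.1) is the surgeon's "decision for or against surgery, typically made by 6 months of age". The surgeon does not see the SRS but does see the clinical MRI report; section 4.3.2 says "Surgeons and families will be aware of these findings and will be able to view the images".

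At operation the study documents the indications, "operative findings at each nerve root, and procedure performed at each nerve root" (4.3.1). Section 4.3.3, in a sentence beginning "For those infants in the study who undergo microsurgical plexus exploration", has the operating surgeon class each root as intact, ruptured or avulsed from its appearance and SSEPs. Sections 4.3.2, 8.2 and 8.4 use these findings only for agreement with MRI, by weighted kappa.

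**The concern.** The objective covers decisions in both directions, but only one direction has an analysis that could give an unfavourable answer. If a non-operated infant does not reach functional scores, the decision against surgery is called into question. If an operated infant's scores rise, nothing separates the effect of the operation from recovery that would have happened anyway.

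This matters beyond a secondary objective. The primary objective speaks of infants who require reconstruction, while the reference standard is the surgeon's decision. Secondary Objective 2 is the plan's stated check on the outcomes of that decision. If the report takes post-operative improvement as confirmation, the surgical class will look validated when it has not been tested. The kappa analysis does not fill the gap, because it evaluates the MRI and not the decision to operate.

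**Working it through.** **1. The plan's number of operated infants.** Section 8.3 assumes a 30% surgical rate and 70 evaluable infants: 0.30 × 70 = 21 operated, 49 not. As a check on that design, take the Hanley-McNeil variance, V(A) = [A(1−A) + (n1−1)(Q1−A²) + (n0−1)(Q2−A²)] / (n1·n0), with Q1 = A/(2−A) and Q2 = 2A²/(1+A). Use the null variance for the critical value and the alternative variance for power. AUC 0.90 against 0.75 at one-sided 5% then needs 72 infants (stated: 70), and power at 21/49 is 78.8%. The stated size is reproduced closely. The point below uses only the 21.

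**2. The two halves of Secondary Objective 2 side by side.**

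| | Against surgery | For surgery |
|---|---|---|
| Hypothesis (2.1.3.1) | Improvement to functional levels | Improvement |
| Analysis (8.4) | Confirm spontaneous recovery at 18 and 30 months | Scores compared with the non-operative group |
| Rule for an unconfirmed decision | Implied: functional level not reached (level undefined) | None |

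**3. What improvement can show.** The change observed in an operated infant is the change due to surgery plus the change that would have occurred without it. The plan observes only the sum. Separating the parts needs the expected course without surgery among infants who meet the indications, and the documents do not give it. Section 1.1 says "60-80% of infants with BPBP will recover spontaneously without surgery", but that covers the whole BPBP population.

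**4. What the group comparison can show.** The indications in 4.2.3 include a Toronto score below 3.5 and an AMS score below 5 for elbow flexion and/or shoulder abduction. The groups are thus separated largely on the scales that are later compared. A difference at 18 or 30 months mixes initial severity with any effect of surgery.

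**5. What the operative data could show, and how precisely.** A per-infant count needs only fields already recorded. With 21 operated infants, the exact (Clopper-Pearson) 95% intervals for the proportion with no ruptured or avulsed root are:

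- 0 of 21: upper limit 1 − 0.025^(1/21) = 0.161, so 0 to 16.1%.
- 2 of 21 (9.5%): 1.2 to 30.4%.
- 4 of 21 (19.0%): 5.4 to 41.9%.

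**6. Illustration only: what unneeded operations could do to the AUC.** Suppose k of the 21 were unneeded; k is an assumption, as the documents give no value.

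- If those infants have SRS values distributed like the non-surgical group and the true AUC is 0.90, observed AUC = [(21−k) × 0.90 + k × 0.50] / 21. This gives 18.5/21 = 0.88 (k=1), 18.1/21 = 0.86 (k=2), 17.7/21 = 0.84 (k=3) and 17.3/21 = 0.82 (k=4).
- If instead the visible MRI prompted those operations and their SRS lies above every non-surgical value, the bias is upward. With a true AUC of 0.80 and a fraction f, observed AUC = (1−f) × 0.80 + f × 1. This gives 0.82 at f = 10% and 0.86 at f = 30%.

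The direction is undetermined and the size rests on assumed inputs.

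**The case against.** The strongest reply is that the protocol claims less than this. Section 2.1.3 speaks of confirming clinical outcomes of decisions, not of proving that surgery was required, and 8.4 applies confirmation only to non-operated infants. That is a fair reading of 8.4. But 2.1.3 names both directions, and 8.4 does not say that the surgical direction has been left out.

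Other parts of the reply stand and limit the point:

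- A reader might infer from the 60-80% figure that operated infants would have improved similarly without surgery. The documents do not support this. Operated infants are selected for failing to recover, and the planned 30% surgical rate lies within the 20-40% that the same figure leaves over.
- A reader might call operated infants without a ruptured or avulsed root false positives in the primary analysis. Under 8.1 they are not: the reference is the surgeon's decision, taken on functional indications. To count them as errors would substitute an anatomical standard that the plan did not choose.
- Nor does the plan record such an infant as a confirmed decision. It has no rule for calling a decision for surgery right or wrong.
- Operative status is itself imperfect. The surgeon who records it has access to the MRI, and 1.1 describes SSEPs as somewhat lacking in specificity.
- Recomputing the AUC after removing operated infants with intact roots would favour the SRS, which is itself a score of root injury. In the illustration with k = 2, removal alone takes the AUC from 0.86 back to 0.90. Verification would also be one-sided, since non-operated infants have no operative findings.

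The plan does have partial safeguards: standard indications, documented reasons for surgery and root-level recording. None yields a per-infant summary of the operated group.

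**Conclusion.** The concern holds in a limited form. As written, the half of Secondary Objective 2 that concerns decisions for surgery has no analysis that could reveal an unneeded operation. Improvement without a threshold or valid comparator cannot be reported as confirming the need for surgery. Data that would allow a descriptive check are collected but not assigned to that purpose.

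The size is unknown. It depends on the course without surgery among infants who meet the indications and on how many operated infants had no ruptured or avulsed root; the documents give neither. The AUC figures of 0.88 to 0.82 show sensitivity to assumed values of k under one assumed SRS distribution, and bias could run either way. They do not show that the primary AUC is biased, and nothing in the documents indicates that k exceeds zero. What changes is the conclusion that the trial may draw about its operated infants, not the primary endpoint.

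**What to change.** **In 8.4**, prespecify as a descriptive check on the surgical reference class, each with an exact 95% interval:

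- the number and proportion of operated infants with at least one ruptured or avulsed root;
- the number and proportion whose procedure included reconstruction.

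State how roots that were not explored or not classified are counted.

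**In 2.1.3**, reword so that AMS and Toronto scores describe post-operative function in operated infants and confirm spontaneous recovery only in non-operated infants. This brings the objective into line with 8.4.

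**Leave the primary AUC as it is.** An AUC that reclassifies infants by root status is better omitted. If kept, label it exploratory, say whether the infants are excluded or moved to the non-surgical class, and note that selecting on root status favours a root-injury score and verifies operated infants only.

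The cost is two lines of analysis and a change of wording, with no new data, visits or change in care. The limitation is precision: with about 21 operated infants, even a clean result of 0 of 21 without rupture or avulsion is compatible with up to 16%. The report should also say that operative status is recorded by a surgeon with access to the MRI.

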3.1 Inclusion Criteria

3.1.1 Diagnosis of brachial plexus birth palsy.

3.1.2 Age at consent ≤ 4 months

3.2 Exclusion Criteria

3.2.1 Bilateral brachial plexus birth palsy.

3.2.2 Age at MRI < 28 days or > 4 months old (patients can be enrolled prior to 28 days of age, but the imaging must occur in the 28 days to 4 months' time period). The lead PI will need to approve the enrollment of a subject who will have the MRI after 90 days of age.

3.2.3 Concomitant medical conditions that would preclude performance of or confound interpretation of MRI or any clinical assessment.

3.3 Number of Subjects
Up to 100 subjects will be enrolled from the three research sites.

3.4 Inclusion of Gender, Minorities, and Vulnerable Populations

3.4.1 Entry into this study is open to patients of both genders.

3.4.2 Entry into this study is open to patients of all ethnic backgrounds.

4.0 Study Design/Procedures:

4.1 General Design

4.1.1 This will be a multicenter prospective cohort study of patients with BPBP. The study will take place at Shriners Hospitals for Children – Northern California, Boston Children's Hospital, and Gillette Children's Specialty Healthcare. MRIs for subjects at SHCNC will be performed at UC Davis Medical Center.

4.1.2 All infants with BPBP between 0 and 12 weeks of age who present for treatment to a participating site will be offered participation in this study. Those infants with concomitant birth injuries that would make positioning in the MRI scanner difficult or painful (such as a birth humerus or clavicle fracture) will have their enrollment deferred. If the injury heals and the MRI can be performed within the required age range, they may be included in the study. If not, they will be excluded. Those infants who attempt to complete or actually complete the MRI scan but end up with unusable images will continue to be followed clinically, but will be removed from participation in this study. Table 1 below shows the visit schedule for study participants and what forms/activities need to be completed at each visit.

Table 1. Schedule of visits.

| Forms/ Activity | Enroll- ment | Follow-up | | | | | |
|--------------------|-----------------|-----------|-------------------------------------|---------------------|-----------------------------|----------|------------------|
| | | Baseline | Study visits until surgery decision | Surgery (if needed) | Study visits until Month 12 | Month 12 | Month 18 (±3 mo) |
| Enrollment | X | | | | | | |
| Patient Assessment | X | X | | X | X | X | X |
| Procedures | | | X | | | | |
| MRI Assessment | X | | | | | | |
| Study Closeout | X* | X* | X* | X* | X* | X* | X |

* If MRI cannot be completed, if patient withdraws, or is lost to follow-up.

